#### 1.3.3 Vitamin D and CLL

Shanafelt and colleagues (63) evaluated the relationship of 25(OH)D serum levels with time-totreatment (TTT) and overall survival (OS) in newly diagnosed CLL patients participating in a prospective cohort study (discovery cohort) and a separate cohort of previously untreated patients participating in an observational study (confirmation cohort). Of 390 CLL patients in the discovery cohort, 119 (30.5%) were 25(OH)D insufficient. After a median follow-up of 3 years, TTT (hazard ratio[HR] = 1.66; P = .005) and OS (HR = 2.39; P = .01) were shorter for 25(OH)D-insufficient patients. In the validation cohort, 61 of 153 patients (39.9%) were 25(OH)D insufficient. After a median follow-up of 9.9 years, TTT (HR = 1.59; P = .05) and OS (HR 1.63; P = .06) were again shorter for 25(OH)D-insufficient patients. On pooled multivariable analysis of patients in both cohorts adjusting for age, sex, Rai stage, CD38 status, ZAP-70 status, immunoglobulin heavy chain variable (IGHV) gene mutation status, CD49d status, and cytogenetic abnormalities assessed by interphase fluorescent in situ hybridization testing, 25(OH)D insufficiency remained an independent predictor of TTT (HR = 1.47; P = .008), although the association with OS was not significant (HR = 1.47; P = .07) (63). There is also anecdotal evidence that consumption of dairy products with higher vitamin D levels decreases absolute lymphocyte counts in patients with CLL (64).

#### 1.3.4 Clinical Data to Date

Amir et al reported the results of a A phase 2 trial exploring the effects of high-dose (10,000 IU/day) vitamin D(3) in breast cancer patients with bone metastases. Forty patients were enrolled. No significant changes in bone resorption markers were seen. Despite no change in global pain scales, there was a significant reduction in the number of sites of pain. A small but statistically significant increase in serum calcium was seen, as was a significant decrease in serum parathyroid hormone (65). Most discussions of the role of vitamin D in cancer therapy express the concern that high-dose calcitriol is too toxic to be administered to patients with cancer. There are now many clinical studies that clearly establish that calcitriol can be safely administered in very high doses if an intermittent treatment schedule is used. Administration of oral calcitriol on a daily schedule (1.5–2.5  $\mu$ g/d, weekly dose intensity ~10.5–17.5  $\mu$ g/wk) is associated with a 20% to 30% frequency of hypercalcemia in men with PCa and in postmenopausal women.(66), (67), (68) and (69)

#### 1.3.3 Clinical Pharmacokinetics

Calcitriol administered by mouth daily for 3 days every week (28  $\mu$ g daily for 3 days) + dexamethasone (4 mg daily for 4 days) weekly is very safe and well tolerated in men with advanced prostate cancer. In 2 studies of patients with advanced prostate cancer, doses of calcitriol of 38  $\mu$ g every day for 3 days weekly and 28  $\mu$ g every day for 3 days monthly were safely administered together with paclitaxel and carboplatin, respectively (70). Fakih and colleagues (71) studied intravenous calcitriol (Calcijex, Roche Pharmaceutical Corporation) weekly + gefitinib and reported that very high doses of calcitriol can be administered safely. The dose-limiting toxicity of weekly intravenous calcitriol + gefitinib was grade 3 hypercalcemia at a dose of 98  $\mu$ g/wk. The phase II dose of this regimen is 77  $\mu$ g weekly alone and 98  $\mu$ g/kg weekly when calcitriol is combined with high-dose dexamethasone.(71) and (72) The systemic exposure 16 of 74

Protocol Version 7 Dated 10/2/2018

of calcitriol following 98  $\mu$ g is approximately 30 ng/h/24 h which is in the range of exposure we have reported in murine models in which calcitriol has clear-cut antitumor activity.(73).

Beer and colleagues (74) have studied high-dose oral calcitriol (as Rocaltrol) and concluded that 0.5  $\mu$ g/kg, weekly is very safe. Studies with DN-101 demonstrated that 45  $\mu$ g weekly was safe and well tolerated and that 165  $\mu$ g given on week 1, followed by 45  $\mu$ g weekly produced no toxicity.(75) A linear relationship between dose of DN-101 administered and area under the curve (AUC) was maintained up to 165  $\mu$ g. Studies using an intermittent schedule of administration (weekly or every day for 3 days weekly) have encountered dose-limiting hypercalcemia only at doses 100  $\mu$ g following intravenous administration; transient increase in serum calcium (11–13 mg/dL) does occur 1 to 3 days after completion of a single or daily for 3 days schedule. However, only at doses achieving AUC more than ~30 ng/h/ml has dose-limiting hypercalcemia been encountered. Hypercalciuria is universal following administration of high-dose calcitriol. Dietary calcium restriction is very difficult for patients to maintain and there is little evidence that it reduces hypercalciuria. There has been no deterioration of renal function in patients receiving high-dose intermittent calcitriol for more than 12 months. Radiographic monitoring for urinary tract stones (ultrasound or computed tomography) in our studies suggests that newly discovered urinary tract stones may occur in 1% to 3% of patients (69).

#### 1.4 **Rationale**

The rationale of this study is built upon the demonstrated safety and biologic activity of both curcumin and vitamin D3 in animal models and human studies. There is no evidence of overlapping toxicities between both agents. Both curcumin and vitamin D3 have demonstrated preclinical activities in CLL and there is preclinical data to suggest potential synergism between both agents: Mosieniak and colleagues have shown that curcumin overcomes the resistance of calcitriol-differentiated HL-60 cells, an acute promyelocytic leukemia cell line, to DNA-damage-induced apoptosis by activating other cell signaling pathways leading to cell death of HL-60; such curcumin-induced cell death did not involve DNA-damage-initiated signaling pathways, to which differentiated HL-60 cells are highly resistant (76). Curcumin, in concentrations as low as 50 µMol increased the expression of VDR in BCR-ABL driven B-ALL murine cells (23). Also, curcumin was shown to directly activate VDR in colon cancer cell lines to induced VDR target genes including CYP3A4, CYP24, p21 and TRPV6 (77). Since both curcumin and vitamin D3, and its analogues, seem to induce cell death through pathways that don't require DNA damage, they have the potential to have clinical activity in 17p/TP53 deleted CLL; a disease that carries a bad prognosis because of resistance to conventional cytotoxic therapeutic agents (31).

We hypothesize that curcumin-vitamin D3 combination would have a synergistic activity against CLL beyond each agent given alone. We hypothesize that this effect is likely related to curcumin upregulating intracellular VDR cells in CLL cells rendering them more susceptible to vitamin D3. We propose to use a curcumin daily dose of 8g as this is dose was shown to have biologic activity, modulation of NF- $\kappa$ B signaling, and steady state pharmacokinetics, and no toxic effects after up to 9 months of therapy (32, 33). We propose to use vitamin D3 daily dose of 10,000 IU as this dose has shown safety and biologic activity in clinical trials of patients with metastatic breast cancer (65). Despite more predictable pharmacokinetics of calcitriol, which made it the more preferred agent in clinical trials for metastatic prostate cancer, we elected to choose vitamin D3 as it has a lower risk for hypercalcemia (66), (67), (68) and (69). As the impact of early 17 of 74 Protocol Version 7 Dated **10/2/2018** 

treatment of CLL on survival remains uncertain, we felt that exposing patients to 20% risk of hypercalcemia with calcitriol therapy is unacceptable under the "do no harm" principle. We propose continuous treatment with both agents analogous to prior clinical trials with curcumin to start 1 week before vitamin D3; for the theoretical advantage of attaining serum steady state of curcumin and upregulating VDR levels in CLL cells making them more susceptible to vitamin D3. We propose an initial duration of treatment of 6 months followed up observation analogous to prior clinical interventions in early stage CLL (78) and analogous to the duration of traditional chemotherapy treatments for advanced CLL (79). At least 4 studies support the concept that maximal cutaneous synthesis of vitamin D (ie, full-body, maximal exposure to sunlight) can be equivalent to an oral vitamin D3 intake of 10,000 IU/day (80-83). Furthermore, a review of data from vitamin D supplementation studies reveals a dose-response curve for vitamin D that is relatively linear up to 10,000 IU of vitamin D3 per day, suggesting that this dose may be a physiologic upper limit (84).

For more than 5 decades, chlorambucil was the standard first-line treatment for CLL and, historically, the overall response rate (ORR) to chlorambucil was 30%. Chlorambucil fell out of favor with the development of purine analogues in the early 1980 but remains an option for elderly frail symptomatic patients who cannot tolerate more forms of aggressive therapy (1). An ORR response rate of 30% had been considered a benchmark for development of CLL therapies after chlormabucil . We rationed that the curcumin/vitamin D3 combination would be worth further clinical development if we observe an ORR response of 30% or better (please refer to section 12.0 for description of response criteria).

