#### 14.2 Sample Size/Accrual Rate

The sample size is calculated for a single arm, Simon optimal 2-stagephase II deign. The design to test the null hypothesis that  $P \le 0.1$  versus the alternative that  $P \ge 0.3$  has a sample size of 29 and a probability of early termination of 0.74 under the null. The power is 0.8 with statistical significance declared at an alpha level of 0.05. An accrual goal of 35 patients will be enrolled in this study to allow 20% ineligibility or drop outs. According to the Simon 2-stage method, 10 patients will be accrued initially during stage I. If there is evidence of clinical benefit, the remaining 25 patients will be enrolled during stage II. For the purpose of stopping the trial for futility, clinical benefit is defined as biologic response or better (please refer to section 12.4 for the definition of biologic response).

In the planned Simon 2-Stage analysis, 10 patients will be enrolled in stage I. An interim analysis will be performed after the 10th patient completes the induction therapy period. If 1 or fewer patients exhibit clinical benefit (biologic response or better), the trial will be stopped. If 2 or more patients demonstrate clinical benefit, the study will proceed to stage II and an additional 19 patients will be enrolled and treated. If the trial goes on to the second stage, a total of 29 eligible patients will be studied. If the total number responding is less than or equal to 5, the drug combination is considered not worth further exploration. The entire study group of 35 patients will be evaluated in the final analysis.

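### Section 1.4 makes an observed response rate of 30% the bar for further development, while the section 14.2 boundary is cleared at 6 of 29 (20.7%), and nothing says which governs

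*Combined protocol and SAP*

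**What the plan says.** Section 1.4 (Rationale) takes 30% from the historical response rate to chlorambucil, describes it as a benchmark for later CLL therapies, and concludes that the combination would merit further development "if we observe an ORR response of 30% or better". It points to section 12.0 for the response criteria.

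Section 14.2 (Sample Size/Accrual Rate) specifies a Simon optimal two-stage design with a null rate of at most 10% and an alternative of at least 30%. The design "has a sample size of 29 and a probability of early termination of 0.74 under the null". On error rates it says: "The power is 0.8 with statistical significance declared at an alpha level of 0.05". On the stages: "In the planned Simon 2-Stage analysis, 10 patients will be enrolled in stage I". The trial stops if at most 1 of those 10 benefits; otherwise 19 more are treated. The final boundary is: "If the total number responding is less than or equal to 5, the drug combination is considered not worth further exploration".

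Section 14.1 defines the primary endpoint as overall response including biologic response as well as CR and PR. Section 2.1 defines ORR by the NCI-WG or Cheson criteria and lists biologic response alongside it.

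**The concern.** The same figure plays two roles. In 14.2, 30% is a property of the unknown true rate: the value at which the design should succeed about 80% of the time. In 1.4 it is a result that has to be seen in the data. A rule calibrated to detect a true rate of 30% must have a boundary below 30%. Otherwise a treatment that works exactly as hoped would fail about half the time.

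Both sentences address whether the combination deserves further development, and no section reconciles them or ranks them. For results between the two bars, the reported conclusion could rest on whichever section is cited, and that choice could be made once the count is known.

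**Working it through.** **Inputs.** From 14.2: p0 = 0.10, p1 = 0.30, n1 = 10, stage I stop at ≤ 1, n = 29 (so 19 in stage II), final boundary r = 5. From 1.4: observed rate ≥ 30%. Sidedness of alpha is not stated; one-sided exact is assumed, as is standard for this design.

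**Step 1: reproduce the stated design.** Early termination under the null:

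P(X1 ≤ 1 | n = 10, p = 0.1) = 0.9^10 + 10 × 0.1 × 0.9^9 = 0.3487 + 0.3874 = 0.736, against the stated 0.74.

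Probability of passing both stages:

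P(go) = Σ over x = 2 to 10 of P(X1 = x) × P(Y ≥ r + 1 − x), with X1 ~ Bin(10, p), Y ~ Bin(19, p), r = 5.

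This gives 0.047 at p = 0.10 (limit 0.05) and 0.805 at p = 0.30 (stated 0.8). An exhaustive search for the Simon optimal design returns the same design: n1 = 10, r1 = 1, n = 29, r = 5.

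**Step 2: turn the 1.4 bar into a count.** 0.30 × 29 = 8.7, so at least 9 responders are needed.

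| Responders of 29 | Observed rate | Clears 14.2 (≥ 6) | Meets 30% |
|---|---|---|---|
| 5 | 17.2% | no | no |
| 6 | 20.7% | yes | no |
| 7 | 24.1% | yes | no |
| 8 | 27.6% | yes | no |
| 9 | 31.0% | yes | yes |

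**Step 3: probability of landing between the bars.** P(6 to 8) is the chance of passing stage I and finishing with 6, 7 or 8 of 29. At p = 0.30 the terms are 0.0662 + 0.1060 + 0.1361 = 0.308. P(≥ 9) uses the Step 1 formula with r = 8 and stage I unchanged.

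| True rate | P(≥ 6), 14.2 rule | P(6 to 8) | P(≥ 9), observed 30% |
|---|---|---|---|
| 0.10 | 0.047 | 0.046 | 0.0014 |
| 0.20 | 0.431 | 0.330 | 0.101 |
| 0.25 | 0.649 | 0.378 | 0.271 |
| 0.30 | 0.805 | 0.308 | 0.497 |
| 0.40 | 0.949 | 0.091 | 0.859 |

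The two right-hand columns add to the first within rounding; for example, 0.308 + 0.497 = 0.805. The 0.25 entry under P(≥ 6) is the sum 0.378 + 0.271.

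**Step 4: dependence on the denominator.** Section 14.2 also says that all 35 patients enter the final analysis. On 35, 30% is 10.5, so 11 responders would be needed (10/35 = 28.6%). The plan gives no boundary for 35, so the 6-to-8 range applies to 29 only.

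**The case against.** The strongest reply is that the sentences do not contradict each other as written. Section 1.4 gives a condition under which development would be worthwhile and does not say it is the only one. Section 14.2 says when to give up and never says that 6 of 29 is enough to proceed. Seven responders would breach neither sentence. This stands. A reader might infer that 1.4 requires 30% and that the two sections return opposite verdicts at 6 to 8 responders, but that adds a converse to each. What remains is a range of results with no agreed conclusion.

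Second, 1.4 is background, and only section 14 has counts, stages and error rates. An analyst would probably follow 14.2. That is likely, but the documents state no order of precedence, and 1.4 speaks explicitly of what is observed.

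Third, the two sentences may count different things. If ORR in 1.4 means CR + PR only, the bars are further apart, and the probabilities above no longer measure the disagreement, because they apply one count to both bars. This also stands.

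Fourth, section 10.5 records that accrual closed on 4/12/2016, so rewording 1.4 now could look like lowering a bar late. Making 14.2 govern does not change the formal test: its boundary is the one to which the stated alpha and power belong.

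Finally, a reader might infer that the trial's real power is 0.50. The documents do not support that. They propose no test at 9 of 29, and the 14.2 rule delivers its stated power.

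**Conclusion.** The point holds as an unreconciled inconsistency between a rationale sentence and the statistical section. The Simon design is not at fault: its early-termination probability, type I error and power all reproduce.

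If both sentences are treated as complete rules for the same endpoint on 29 patients, 6 to 8 responders clear one bar and miss the other. The chance of that is about a third at true rates of 20% to 30%, and small (4.6%) at the null. On the literal reading the same results simply lack an agreed conclusion. Either way the plan should settle the matter before the result is interpreted, because enforcing the 1.4 bar would reduce the chance of success at the targeted rate from 0.805 to 0.497.

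The sizes rest on a denominator of 29, a single response definition in both sections, and the stage I rule applied as written.

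**What to change.** In section 1.4, replace the clause on observing 30% or better with wording to this effect: *30% is the targeted true response rate; the go/no-go decision follows the boundary in section 14.2, that is, 6 or more responders among 29 evaluable patients on the primary endpoint defined in section 14.1, which includes biologic response.* If the chlorambucil benchmark is kept, say that it refers to CR + PR and is context only, not the decision threshold.

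The cost is a sentence or two in the rationale. Sample size, the stage I rule, the formal test and patient management are unchanged.

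This edit does not settle two neighbouring matters, which need their own reconciliation: whether the final analysis uses 29 or 35 patients (14.2), and whether ORR includes biologic response (2.1 against 14.1).

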# 2.0 OBJECTIVES

To determine the efficacy, and tolerability, of curcumin and vitamin D3 combination in patients with early stage, untreated, chronic lymphocytic leukemia (CLL) or small lymphocytic lymphoma (SLL).

#### 2.1 **Primary Objective**

To determine the overall response rate (ORR) based on NCI-WG criteria in CLL or the Cheson criteria in SLL. Will also examine biologic response rate (78); defined as at least 20% reduction of absolute lymphocyte count (ALC) that is sustained over 2 months or  $a \ge 30\%$  reduction in palpable lymphadenopathy using this regimen.

#### 2.2 Secondary Objective(s)

To determine the Time to first cytotoxic treatment (TFCT), progression free survival (PFS), and Overall survival (OS) using this regimen.

# 3.0 STUDY DESIGN

#### 3.1 Study design

This is Case Comprehensive Cancer Center open label phase II trial.

# CASE **5913**

Protocol Version 7 Dated 10/2/2018

#### 3.2 Number of Subjects

We plan to enroll a maximum of 35 patients to obtain 29 evaluable patients (assuming a 20% dropout rate).

#### 3.3 **Replacement of Subjects**

All subjects who have received at least one dose of study agent, but have discontinued study agent prior to the first scheduled response assessment are evaluable for toxicity, but are not evaluable for study endpoints. Subjects need to have received at least 2 cycles of treatment to evaluable for response. Therefore, subjects who are not evaluable for study endpoints may be replaced.

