# 6.4 **Duration of Follow Up**

**30-Day Follow-Up**: Patients will be followed for toxicity for 30 days after treatment has been discontinued or until death, whichever occurs first.

**Long term Follow-Up**: Patients will be followed, every 3-6 months (as clinically indicated), for 2 years after discontinuation of study medications for long-term outcomes.

The clinical course of each event will be followed until resolution, stabilization, or until it has been determined that the study treatment or participation is not the cause.

Serious adverse events that are still ongoing at the end of the study period will necessitate follow-up to determine the final outcome. Any serious adverse event that occurs after the study period and is considered to be possibly related to the study treatment or study participation will be recorded and reported immediately.

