#### **12.6 Progression-free survival (PFS)**

Progression-free Survival (PFS) is defined as the time from entry onto study until CLL/SLL progression or death from any cause. PFS is often considered the preferable endpoint in lymphoma clinical trials, especially those involving incurable histologic subtypes (e.g., follicular and low grade, mantle cell lymphoma). PFS reflects tumor growth and, therefore, occurs prior to the endpoint of overall survival. In addition, PFS is not confounded by the administration of subsequent therapy. Whether a prolongation of PFS represents direct clinical benefit or a surrogate for clinical benefit depends on the magnitude of the effect and the risk-benefit ratio of the therapy under investigation. Unlike survival, the precise date of progression is generally unknown. It may be defined as the first date of documentation of a new lesion or enlargement of a previous lesion, or the date of the scheduled clinic visit immediately after radiologic assessment has been completed. Where there is missing information, censoring of the data may be defined as the last date at which progression status was adequately assessed.

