## 14.3 Analysis of Secondary Endpoints

The secondary endpoints include Time to first cytotoxic treatment (TFCT), progression free survival (PFS) and overall survival (OS). For those time-to-event endpoints, Kaplan-Meier method and Cox proportional hazard model will be used for the data analysis. Potential prognostic factors will be correlated with conversion status by Fisher's exact test or Chi-square test, logistic regression will be used to assess the effect on conversion from the combination of multiple factors.

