#### 14.4.2 Evaluation of response:

Subjects need to have received 2 or more cycles of treatment to be evaluable for response. Each patient will be assigned one of the following categories: 1) complete response, 2) partial response, 3) stable disease, 4) progressive disease, 5) early death from malignant disease, 6) early death from toxicity, 7) early death because of other cause, or 9) unknown (not assessable, insufficient data). [Note: By arbitrary convention, category 9 usually designates the "unknown" status of any type of data in a clinical database.]

All of the patients who met the eligibility criteria (with the possible exception of those who received no study medication) should be included in the main analysis of the response rate. Patients in response categories 4-9 should be considered to have a treatment failure (disease progression). Thus, an incorrect treatment schedule or drug administration does not result in exclusion from the analysis of the response rate.

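### Section 3.3 takes early discontinuers out of all study endpoints, section 14.2 keeps all 35 patients, and 14.3 names no population for TFCT, PFS or OS; following 3.3 would bias PFS upward, probably by a small amount

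*Combined protocol and SAP*

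**What the plan says.** Section 3.3 states that treated subjects who stop before the first scheduled response assessment "are evaluable for toxicity, but are not evaluable for study endpoints". A separate sentence then deals with response: "Subjects need to have received at least 2 cycles of treatment to evaluable for response". The paragraph ends by allowing replacement: "subjects who are not evaluable for study endpoints may be replaced".

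The secondary endpoints in 2.2, 14.1 and 14.3 are TFCT, PFS and OS. Section 12.6 sets the PFS clock: "Progression-free Survival (PFS) is defined as the time from entry onto study until CLL/SLL progression or death from any cause". Section 12.7 gives TFCT the same starting point. No section defines OS or its time origin.

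Three other places bear on who is analysed:

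- Section 14.2 closes by saying that the whole group of 35 is evaluated in the final analysis.
- Section 14.4.2 says that all eligible patients, possibly except those never treated, "should be included in the main analysis of the response rate". It counts early deaths and unknowns as failures, and it covers the response rate only.
- Section 14.3 names Kaplan-Meier and Cox methods for the time-to-event endpoints but no population.

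Follow-up does not stop with treatment. Section 6.4 says: "Patients will be followed, every 3-6 months (as clinically indicated), for 2 years after discontinuation of study medications for long-term outcomes". It makes no exception for early discontinuers.

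**The concern.** Section 3.3 uses the general term for endpoints and handles response in its own sentence, so the exclusion cannot be assumed to concern response alone. Read literally, an early discontinuer also leaves the TFCT, PFS and OS analyses and may be replaced by someone who stays on treatment.

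For PFS and TFCT that would make membership of the cohort depend on something that happens after the clock has started (guarantee-time bias). For PFS the link is direct. Section 6.3 lists disease progression and death among the reasons for ending treatment, so the event being counted can itself remove the patient from the count. Such events can be recorded early: section 11.1.2 schedules blood counts at Cycle 1 Day 8 and Cycle 2 Day 1 and node measurements at Cycle 2 Day 1, and section 12.1 counts a lymphocyte rise above 50% (to at least 5,000/µL) or new palpable nodes as progression.

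At stake is whether two analysts working from the same document would draw the same curves, and whether one of the permitted curves is too favourable.

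**Working it through.** **The plan's own figures.** None is given for TFCT, PFS or OS. The response design does reproduce: with at most 1 of 10 to stop and at most 5 of 29 to fail, exact binomial calculation gives a probability of early termination of 0.736 at a response rate of 0.1, alpha 0.047 and power 0.805, against the stated 0.74, 0.05 and 0.8. This point does not touch those figures.

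**Inputs.**

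- Cycle length is 28 days (section 6.0), so two cycles are 56 days, or 56/30.4375 = 1.84 months.
- 35 enrolled and 29 evaluable (section 3.2), a gap of 6.
- Median OS in early-stage disease is 8 to 12 years (section 1.1).
- PFS and TFCT medians are not in the documents. I assume 12, 24 and 60 months.
- A 56-day cut is also an assumption. The only visit with a stated response purpose is the Cycle 3 Day 1 CT, in a subset of SLL patients; no first response assessment is named for CLL.

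**Model.** Suppose event times are exponential, everyone with an event in the first 56 days is dropped, and time still runs from entry. The reported curve is then S(t)/S(56 days) instead of S(t), with S(t) = 2^(−t/median), and the median rises by about 1.8 months.

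| Assumed median | S(56 d) | Expected events by day 56, of 35 | 24-month estimate, all patients | 24-month estimate under 3.3 | Shift (points) |
|---|---|---|---|---|---|
| 12 months (PFS/TFCT) | 0.8992 | 3.5 | 0.250 | 0.278 | +2.8 |
| 24 months (PFS/TFCT) | 0.9483 | 1.8 | 0.500 | 0.527 | +2.7 |
| 60 months (PFS/TFCT) | 0.9790 | 0.7 | 0.758 | 0.774 | +1.6 |
| 96 months (OS) | 0.9868 | 0.5 | 0.841 | 0.852 | +1.1 |
| 144 months (OS) | 0.9912 | 0.3 | 0.891 | 0.899 | +0.8 |

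If the cut fell at Cycle 2 Day 1 (28 days, 0.92 months), the shift would be about half. For a 12-month median, 0.250 × 2^(0.92/12) = 0.264, or +1.4 points.

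**Range outside the model.**

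- Zero: if the excluded patients have no early event and the same later prognosis, the estimate is unchanged on average.
- Extreme: if all 6 of the 35 − 29 allowance were early events and the true 24-month PFS were 0.70, the reported value would be 0.70/(29/35) = 0.845.
- Between: if 29 patients have an assumed 24-month PFS of 0.75 and the 6 excluded have q, the all-treated value is (29 × 0.75 + 6q)/35. This is 0.621 at q = 0, 0.707 at q = 0.5 and 0.750 at q = 0.75, so the overstatement runs from 13 points through 4 to none. It is set entirely by q.

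**The case against.** The strongest reply is that 14.2 already settles the matter: all 35 are evaluated, and that number includes the allowance for ineligible patients and drop-outs. Section 3.3 can also be read narrowly. Its exclusion turns on a response assessment, the next sentence is about response, replacement follows from that, and 3.2 uses the word evaluable for the 29 patients of the response design. TFCT, PFS and OS are never mentioned there.

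Much of this stands. A reader might infer that the plan definitely estimates all three endpoints only in patients who lasted two cycles, with curves flat for eight weeks. The documents do not support that: 14.2 points the other way, 14.3 is silent, and the cut is undefined for CLL. Nor is entry a documented origin for OS.

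It does not remove the problem, however. The sentence in 14.2 closes a paragraph on response cut-offs, does not mention time-to-event endpoints and does not say that it overrides 3.3.

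The reply is also right on consequence. These are single-arm secondary estimates with no benchmark or decision rule. Patients with an indication for treatment are excluded (4.2.2), and no grade 3-4 toxicity is expected (6.1, 7.0), so early events should be few.

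**Conclusion.** Wrong as written. Sections 3.3 and 14.2 give incompatible populations, no section says which governs TFCT, PFS and OS, and one of the two stated rules yields biased secondary estimates.

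The upward direction is firm for PFS if 3.3 is applied and any excluded patient progresses or dies early. For TFCT and OS it depends on what happens to the excluded patients; someone who stops for toxicity or by choice may have no early event.

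The likely size is about 2 to 3 points at 24 months for PFS or TFCT and about 1 point for OS. This rests on the exponential model, a 56-day cut and, for PFS and TFCT, assumed medians. A reader might infer that all three endpoints are overstated by 4 to 13 points. That range requires the excluded patients to have a 24-month PFS of 0 to 50% against 75% in the rest, and it treats the whole gap between 35 and 29 as early discontinuers, although 14.2 says that the allowance also covers ineligibility. The documents support neither assumption. The response-based decision rule is unaffected.

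**What to change.** Four text changes:

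1. In 3.3, limit non-evaluability and replacement to a supportive analysis of response-evaluable patients.
2. In 14.3, state that TFCT, PFS and OS are estimated from study entry in every patient who took at least one dose of either agent, whether or not replaced, with usual censoring. Naming either agent matters because vitamin D3 starts a week after curcumin.
3. In section 12 or 14.3, give study entry as the time origin for OS.
4. Reconcile 3.3 with 14.2 and 14.4.2, so that one statement says which patients each analysis counts, including any treated patient later found ineligible.

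Section 10.5 records that accrual closed in 2016, so this affects analysis text only. The follow-up in 6.4 should already supply the data, except for patients who withdrew from the study altogether; they would be censored when last assessed. The cost is a few sentences and possibly slightly less favourable reported figures.
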